9 PATIENT AND PUBLIC INVOLVEMENT (PPI)

The impact of changes in acidity on clinical outcome and cardiac function has been examined in small numbers of patients in the past. However, its relevance to the monitoring and treatment of larger number of patients is unclear. This study should provide important information using a large cohort of patients.

10 FUNDING AND SUPPLY OF EQUIPMENT

The study funding has been reviewed by the KCH R&I Office, and deemed sufficient to cover the requirements of the study.

THIS STUDY IS NOT FUNDED

11 DATA HANDLING AND MANAGEMENT

Where data will be recorded: initially on paper with a reference code for each patient. On enrolment the patient is given a unique study ID. This usually has a numeric code for the site as well as a sequential number for patients e.g 23-001, 23-002 etc. the case report forms (data collection forms) only have study ID on. There is no patient ID at all on the CRF, but we have an enrolment log- just a list of name, hospital number and study ID.

12 MATERIAL/SAMPLE STORAGE

There is usually a copy of this in the site file and on our network drive. This is only accessible by appropriate hospital staff and outside researchers only if patient consents. Therefore research team knows who the number relates to and could trace back if necessary but no-one else. This is why we refer to an enrolment log in the IRAS form because we need some way of linking patients to data.

- If samples will be stored for future use (and the details): data will be store for about six months. There is usually a copy of this in the site file and on our network drive.
- Measures for the processing, control and safe storage of samples: no tissue samples.
- Details of data controller/custodian. It will be Chief investigator , myself ([name])

NOT APPLICABLE :In the study, will be collected from patients in accordance with the patient consent form and patient information sheet and shall include all tissue samples or other biological materials and any derivatives, portions, progeny or improvements as well as all patient information and documentation supplied in relation to them. Samples will be processed, stored and disposed in

Full title of the research: **The impact of systemic pH on cardiac function and clinical outcome in the critically ill patient.**

IRAS Project ID: **227870**

accordance with all applicable legal and regulatory requirements, including the Human Tissue Act 2004 and any amendments thereafter.

13 PEER AND REGULATORY REVIEW

The study has been peer reviewed in accordance with the requirements outlined by KCH R&I.

Choose either (having discussed with the KCH R&I Office):

- This study has been peer reviewed within KCH/KCL, by an independent and relevant peer reviewer/committee (amend as required) on (insert date). The Sponsor has accepted these reviews as adequate evidence of peer review.

14 ASSESMENT AND MANAGEMENT OF RISK

No applicable

15 RECORDING AND REPORTING OF EVENTS AND INCIDENTS

16.1 Definitions of Adverse Events

Term	Definition
Adverse Event (AE)	Any untoward medical occurrence in a patient or study participant, which does not necessarily have a causal relationship with the procedure involved.
Serious Adverse Event (SAE).	Any adverse event that: 
 • results in death, • is life-threatening*, • requires hospitalisation or prolongation of existing hospitalisation**, • results in persistent or significant disability or incapacity, or • consists of a congenital anomaly or birth defect

*A life- threatening event, this refers to an event in which the participant was at risk of death at the time of the event; it does not refer to an event which hypothetically might have caused death if it were more severe.
 
** Hospitalisation is defined as an in-patient admission, regardless of length of stay. Hospitalisation for pre-existing conditions, including elective procedures do not constitute an SAE.
	

15.2 Assessments of Adverse Events

Each adverse event will be assessed for severity, causality, seriousness and expectedness as described below.

Full title of the research: **The impact of systemic pH on cardiac function and clinical outcome in the critically ill patient.**

IRAS Project ID: **227870**

16.2.1 Severity: NOT APPLICABLE

The generic categories below are given for use as a guide. You may have a more specific scale that you want to use related to the disease (e.g. CTCAE criteria).

Category	Definition
Mild	The adverse event does not interfere with the participant's daily routine, and does not require further procedure; it causes slight discomfort
Moderate	The adverse event interferes with some aspects of the participant's routine, or requires further procedure, but is not damaging to health; it causes moderate discomfort
Severe	The adverse event results in alteration, discomfort or disability which is clearly damaging to health

16.2.2 Causality: N/A. NOT APPLICABLE

The assessment of relationship of adverse events to the procedure is a clinical decision based on all available information at the time of the completion of the case report form.

If a differentiated causality assessment which includes other factors in the study is deemed appropriate, please add/amend the following wording to specify:

It is of particular importance in this study to capture events related to the product application procedure (specify e.g. surgery) / product failure / mandatory concomitant medications (specify e.g. conditioning chemotherapy). The assessment of relationship of an adverse event to this/these additional safety issue(s) will also be carried out as part of the study.

The differentiated causality assessments will be captured in the study specific CRF/AE Log and/or SAE form (amend as required).

The following categories will be used to define the causality of the adverse event:

Category	Definition
Definitely:	There is clear evidence to suggest a causal relationship, and other possible contributing factors can be ruled out.
Probably:	There is evidence to suggest a causal relationship, and the influence of other factors is unlikely

Full title of the research: **The impact of systemic pH on cardiac function and clinical outcome in the critically ill patient.**

IRAS Project ID: **227870**

Possibly	There is some evidence to suggest a causal relationship (e.g. the event occurred within a reasonable time after administration of the study procedure). However, the influence of other factors may have contributed to the event (e.g. the participant's clinical condition, other concomitant events).
Unlikely	There is little evidence to suggest there is a causal relationship (e.g. the event did not occur within a reasonable time after administration of the study procedure). There is another reasonable explanation for the event (e.g. the participant's clinical condition).
Not related	There is no evidence of any causal relationship.
Not Assessable	Unable to assess on information available.

16.2.3 Expectedness: N/A. NOT APPLICABLE from the observational study

Category	Definition
Unexpected	An adverse event which is not consistent with the information about the procedure listed in the manual of operation or clearly defined in this protocol.

* this includes listed events that are more frequently reported or more severe than previously reported

15.3 Recording adverse events: N/A

NOT APPLICABLE. COLLECTION OF DATA ONLY

15.4 Procedures for recording and reporting Serious Adverse Events: N/A. NOT APPLICABLE

All serious adverse events will be recorded in the medical records and the CRF, and the sponsor's AE log. All SAEs (except those specified in section 16.5 as not requiring reporting to the Sponsor) must be recorded on a serious adverse event (SAE) form. The CI/PI or designated individual will complete an SAE form and the form will be preferably emailed to the Sponsor within 5 working days of becoming aware of the event. The Chief or Principal Investigator will respond to any SAE queries raised by the sponsor as soon as possible.

Where the event is unexpected and thought to be related to the procedure this must be reported by the Investigator to the Health Research Authority within 15 days.

[figure not shown]
Full title of the research: **The impact of systemic pH on cardiac function and clinical outcome in the critically ill patient.**

IRAS Project ID: **227870**

Full title of the research: **The impact of systemic pH on cardiac function and clinical outcome in the critically ill patient.**

IRAS Project ID: **227870**

Flow Chart for SAE reporting

16.5 Serious Adverse Events that do not require reporting

It is an observational study. We do not expect any incident. There are not interventions at all. If a SAE occurs (from PiCCO monitoring use) will report to the Clinician Consultant in charge who is at the end the final responsible of the patient and the responsible of putting the PiCCO monitoring on the patient.

15.6 Reporting Urgent Safety Measures

If any urgent safety measures are taken the CI/ PI shall immediately and in any event no later than 3 days from the date the measures are taken, give written notice to the relevant REC and Sponsor of the measures taken and the circumstances giving rise to those measures.

15.7 Protocol deviations and notification of protocol violations

A deviation is usually an unintended departure from the expected conduct of the study protocol/SOPs, which does not need to be reported to the sponsor. The CI will monitor protocol deviations.

A protocol violation is a breach which is likely to effect to a significant degree –

- (a) the safety or physical or mental integrity of the participants of the study; or
- (b) the scientific value of the study.

The CI and sponsor will be notified immediately of any case where the above definition applies during the study conduct phase.

16.8 Reporting incidents involving a medical device

Any adverse incident involving a medical device should be reported to the manufacturer of the device.

This is especially important where the incident has led to or, was it to occur again could lead to an event classified as serious (see section 9.1 for definition of SAE). Other minor safety or quality problems should be reported along with incidents that appear to be caused by human error.

All adverse incidents must be reported by the Clinician Consultant responsible of the patient. The study is only observational and there are not interventions or decisions involving the use of the PiCCO device. That decision will be made by the Clinical Consultant in charge in the ICU therefore incidents should be reported as soon as possible (usually within 24 hours) as per protocol in the Trust.

Adverse incidents related to a medical device can be reported directly to the MHRA via the online system (www.mhra.gov.uk). Alternative contact details: Medicines & Healthcare products Regulatory Agency Adverse Incident Centre ([contact]; [contact]).

Local trust reporting procedures may also need to be followed. It is the responsibility of the PI and study site team to ensure they are aware of any specific local requirements for reporting device incidents.

15.9 Trust incidents and near misses. NOT APPLICABLE from the observational study

An incident or near miss is any unintended or unexpected event that could have or did lead to harm, loss or damage that contains one or more of the following components:

- a. It is an accident or other incident which results in injury or ill health.
- b. It is contrary to specified or expected standard of patient care or service.
- c. It places patients, staff members, visitors, contractors or members of the public at unnecessary risk.
- d. It puts the Trust in an adverse position with potential loss of reputation.
- e. It puts Trust property or assets in an adverse position or at risk.

Incidents and near misses must be reported to the Trust through DATIX as soon as the individual becomes aware of them.

A reportable incident is any unintended or unexpected event that could have or did lead to harm, loss or damage that contains one or more of the following components:

- a) It is an accident or other incident which results in injury or ill health.
- b) It is contrary to specified or expected standard of patient care or service.
- c) It places patients, staff members, visitors, contractors or members of the public at unnecessary risk.
- d) It puts the Trust in an adverse position with potential loss of reputation.
- e) It puts Trust property or assets in an adverse position or at risk of loss or damage.

16 MONITORING AND AUDITING

The Chief Investigator will ensure there are adequate quality and number of monitoring activities conducted by the study team. This will include adherence to the protocol, procedures for consenting and ensure adequate data quality.

The Chief Investigator will inform the sponsor should he/she have concerns which have arisen from monitoring activities, and/or if there are problems with oversight/monitoring procedures.

17 TRAINING

The Chief Investigator will review and provide assurances of the training and experience of all staff working on this study. Appropriate training records will be maintained in the study files

The training section may also include:

- Specific training requirements for staff working on the project: NOT APPLICABLE
- Specific qualifications and experience required of staff on the project: SENIOR ICU STAFF
- Identifying if training may require a renewal at any point throughout the study: NOT APPLICABLE

18 INTELLECTUAL PROPERTY: N/A. NOT APPLICABLE**19 INDEMNITY ARRANGEMENTS**

KCH will provide NHS indemnity cover for negligent harm, as appropriate and is not in the position to indemnify for non-negligent harm. NHS indemnity arrangements do not extend to non-negligent harm and NHS bodies cannot purchase commercial insurance for this purpose; it cannot give advance undertaking to pay compensation when there is no negligence attributable to their vicarious liability. The Trust will only extend NHS indemnity cover for negligent harm to its employees, both substantive and honorary, conducting research studies that have been approved by the R&D Department. The Trust cannot accept liability for any activity that has not been properly registered and Trust approved. Potential claims should be reported immediately to the Joint Research Office.

20 ARCHIVING

Date of birth	
Sex (M/F)	
Hospital ADMISSION date	
ICU ADMISSION date	

 • Unplanned/emergency admission. • Planned /elective admission. 	
ICU DISCHARGE date	
Discharged alive from ICU?	(Y / N)

 • From ICU to home directly. • From ICU to hospital ward. • From ICU to another ICU (other hospital) 	
Discharged alive from HOSPITAL?	(Y / N)

 • Home • Nursing home or equivalent 	
28-day mortality. Death occurring within 28 days of hospital discharge?	(Y / N)
Admitting diagnosis group:	

 • Cardiac arrest/ other causes of cardiogenic shock • Cardiothoracic surgery • Septic shock 
 ➢ Medical ➢ Neutropenic sepsis/ other haematology & oncology sepsis ➢ Surgical • Post-operative management: any other speciality 	

 • Haemorrhagic shock 
 ➢ Major trauma ➢ Gastrointestinal/other medical ➢ Post-surgical • Acute respiratory failure 
 ➢ COPD /asthma exacerbation ➢ Pneumonia ➢ Other causes • Acute renal failure requiring hemofiltration • Trauma/neuro-surgical • Decompensated liver disease/ acute liver failure • Diabetic ketoacidosis/hyperosmotic syndrome • Others 	

PATIENT RESEARCH ENCRYPTED CODE:
	

Chronic diseases
 
 • Ischaemic heart disease. • Congestive heart failure • Atrial fibrillation/Atrial flutter • Devices 
 ➢ Pacemaker (PM) +/- Implantable cardioverter-defibrillator (ICD) ➢ Cardiac resynchronization therapy (CRT) +/- (ICD) • Arterial hypertension • Pulmonary hypertension • Pulmonary embolus/deep vein thrombosis • COPD/Asthma • Fibrosis • Diabetes mellitus • End stage kidney disease (on regular dialysis) • Chronic kidney disease or pre-dialysis (NOT on dialysis) • Liver disease • Morbid obesity. • Recent quimiotherapy / radiotherapy (last 30 days) • Haematology malignancies 
 ➢ Acute myeloid leukaemia (AML) ➢ Chronic lymphocytic leukaemia (CLL) ➢ Myeloma ➢ Lymphoma • Other hemato-onco malignancies 	

Severity scores
 
 • APACHE II 	

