2 BACKGROUND AND RATIONALE

3 OBJECTIVES

Goals

Primary

1. Assess whether there are significant changes in cardiac function associated with changes in blood pH.
2. Relate the changes in cardiac function to presence or absence of underlying cardiac disease.

Secondary

3. To establish which factors affected by blood pH have an impact on cardiac function.

Full title of the research: **The impact of systemic pH on cardiac function and clinical outcome in the critically ill patient.**

IRAS Project ID: **227870**

4. Study the mortality of patients admitted to the Intensive Care Unit (ICU) who had continuous cardiac monitoring at any time during their admission and relate it to changes in blood pH.

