8 STATISTICAL METHODS

The description of quantitative variables is carried out with central tendency and dispersion indices, whether based on values (mean and standard deviation) or on ordinations (median and interquartile range) according to whether they meet normality or not, respectively. Its graphic representation is done with Histograms and Cash Diagrams. The description of categorical variables is performed with absolute and relative frequencies in percentages. Its graphic representation is done with bar charts.

The relationship between categorical variables is analyzed by comparing proportions with the Pearson Chi-square test, provided that there are less than 20% of squares in the contingency table with expected frequencies less than 5. In the case that there is more 20% of squares with expected frequencies less than 5, the Fisher's exact test is used bilaterally.

Full title of the research: **The impact of systemic pH on cardiac function and clinical outcome in the critically ill patient.**

IRAS Project ID: **227870**

The magnitude of the effect of the relationship between two binary variables has been analyzed with the Ratios of proportions or Relative Risk and with the Odds Ratio.

The relationship between a binary exposure variable and a quantitative response is analyzed with the Student-Fisher t test for independent samples if the normality condition is met. According to whether or not the equality of variances are met, the Student-Fisher t test is used for independent groups for homogeneous variances or for non-homogeneous variances, respectively. In case of not fulfilling the condition of normality, the comparison of two means is made with the non-parametric Mann-Whitney U test.

The comparison between a polytomic predictor and a quantitative response is made through the analysis of variance (ANOVA) in the case of meeting the conditions of normality and homogeneity of variances. If any of these conditions is not met, it is done with the non-parametric H test of Kruskal-Wallis. If the polytomic predictor is ordinal, the ANOVA trend test or the non-parametric Jonckheere-Terpstra trend test is also used, depending on whether normality is met or not, respectively.

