The relationship between two independent quantitative variables is evaluated with the correlation coefficient r of Pearson if normality is met, or with the nonparametric correlation coefficient ρ of Spearman if normality is not met. Its graphic representation is made with the scatter diagrams or points.

Full title of the research: **The impact of systemic pH on cardiac function and clinical outcome in the critically ill patient.**

IRAS Project ID: **227870**

Normality is assessed with the Kolmogorov-Smirnov test with the Lilliefors significance correction for large samples, or with the Shapiro-Wilks test for small samples. The equality of variances is analyzed with the Levene variance homogeneity test.

The relationship between two related quantitative variables is performed using the Student-Fisher t-test for related samples in case the normality condition is met. Otherwise, the non-parametric Wilcoxon T test is used. The relationship between two paired categorical variables is performed by the McNemar symmetry test.

The relationship between a continuous quantitative response and one or several predictors, whether binary, polytomic or quantitative, is done with Simple or Multiple Linear Regression respectively.

The polytomous predictors variables are introduced in the Linear Regression models broken down into binary indicator variables coded with respect to the first reference category.

An estimative multivariate linear regression model of the effect of the predictor Change of pH (between the lowest and highest pH) on the response Change in cardiac output (corresponding to the moments between the lowest and the highest pH) has been performed. The possible role as confounding factors of several variables on this relationship has been evaluated. A predictive multivariate model of linear regression has been performed to evaluate the factors that intervene in the Cardiac Contractility.

Full title of the research: **The impact of systemic pH on cardiac function and clinical outcome in the critically ill patient.**

IRAS Project ID: **227870**

Both the predictive and the estimative models have been carried out with the manual backward step procedure using the criterion of decreasing statistical significance to establish the order to evaluate the withdrawal or permanence of each predictor.

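### The item labelled 28-day mortality leaves out every in-hospital death if completed as worded, and the plan offers only unadjusted tests for relating death to pH (secondary goal 4)

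*Combined protocol and SAP*

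**What the plan says.** **Death fields.** The form under Section 20 has three yes/no items on death: alive at ICU discharge, alive at hospital discharge ("Discharged alive from HOSPITAL"), and a third worded "28-day mortality. Death occurring within 28 days of hospital discharge". It also offers "From ICU to another ICU (other hospital") as a destination on leaving the ICU. As printed, it has no date of death and no hospital discharge date. It stops at APACHE II, so further pages may exist.

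**Goal 4.** Section 3 (repeated in the Study Summary) sets out to study the mortality of ICU patients "who had continuous cardiac monitoring at any time during their admission and relate it to changes in blood pH". It gives no time point, time origin or death field.

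**Methods.** The methods appear three times: in the Study Summary, Section 4 and Section 8.
- Categorical variables are compared by chi-square or Fisher's exact test. "The magnitude of the effect of the relationship between two binary variables has been analyzed" by relative risk and odds ratio.
- Quantitative variables are compared between two groups by t test or Mann-Whitney.
- Regression is for one case only: "The relationship between a continuous quantitative response and one or several predictors" is handled by linear regression. The two multivariable models named have change in cardiac output and cardiac contractility as responses.
- No logistic or survival model appears in any copy.

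**Severity and age.** APACHE II, date of birth and ICU admission date are on the form. No analysis of death is said to use them.

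**The concern.** Two things are wrong as written.

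1. **The label and definition of the third item disagree.** The label suggests all deaths within 28 days of a common starting point. The definition starts the clock at hospital discharge, so only patients who leave alive can score yes. Staff in seven ICUs could complete it in different ways, and a percentage reported under the label would not be 28-day mortality in the usual sense.

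2. **Death gets only crude tests.** Sicker patients are more likely both to have disturbed pH and to die. An unadjusted association between pH change and death therefore cannot be read as evidence about pH. The plan recognises this for cardiac output, where it assesses confounders, but not for death.

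The study title promises a finding on clinical outcome, and mortality is the only clinical outcome among the goals.

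**Working it through.** **Step 1: the item against its neighbours.**

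| Patient | Alive at ICU discharge | Alive at hospital discharge | Item labelled 28-day mortality, read literally |
|---|---|---|---|
| Dies in ICU | N | N | cannot be Y (never discharged alive) |
| Dies on ward | Y | N | cannot be Y |
| Dies within 28 days after leaving hospital | Y | Y | Y |
| Survives beyond that | Y | Y | N |

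The item misses all in-hospital deaths. The two adjacent fields capture them.

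**Step 2: which listed methods can take death as the outcome.**

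| Method in the plan | Usable for death? | Adjusts for severity? |
|---|---|---|
| Chi-square/Fisher, relative risk, odds ratio | Yes, if pH change is dichotomised | No |
| t test/Mann-Whitney | Yes, with death as the grouping variable (the reverse of goal 4) | No |
| Linear regression, including both named models | No, continuous response only | – |

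**Step 3: how much crude testing could matter.** The plan states no mortality rate, effect size or power for goal 4, so there is no figure to reproduce. What follows is an illustration.

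- From the documents: n = 346 (Section 4) and significance at P < 0.05 (Section 8).
- Assumed: 30% mortality (346 × 0.30 ≈ 104 deaths); severity S standard normal; logit P(death) = a + b·S with b = 0.3, 0.5, 0.8 or 1.0 and a = −0.864, −0.893, −0.959 or −1.015 to hold mortality at 30%.
- Assumed: pH exposure X = ρ·S + √(1−ρ²)·noise, with ρ = 0.1 to 0.4. X has no effect on death.
- Assumed: the measured severity score correlates 0.7 with S.
- 2,000 simulated studies per cell. Each entry is the percentage with P < 0.05 for X, shown as crude t test / logistic regression adjusted for the score.

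| b (log-odds per SD) | ρ = 0.1 | ρ = 0.2 | ρ = 0.3 | ρ = 0.4 |
|---|---|---|---|---|
| 0.3 | 5 / 4 | 7 / 5 | 11 / 7 | 16 / 7 |
| 0.5 | 7 / 6 | 14 / 7 | 22 / 9 | 37 / 14 |
| 0.8 | 8 / 6 | 22 / 10 | 43 / 14 | 68 / 26 |
| 1.0 | 11 / 7 | 29 / 11 | 57 / 21 | 83 / 34 |

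Checks: with ρ = 0 the crude test rejects in 4–6% of studies, as it should. Adjusting for true severity gives 4–6% throughout. The simulation standard error near 35% is √(0.35 × 0.65/2000) ≈ 1.1 percentage points, so the adjusted range is best read as about 4–35%.

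**Step 4: if the exposure is a change in pH.** Suppose sicker patients start more acidotic and later drift back towards average. Last-minus-first pH is then linked to severity through the first value. Assumptions: no pH effect beyond severity; severity–first-pH correlation −0.3 or −0.5; first–last correlation 0.3 or 0.6; score correlation 0.7; b = 0.5 to 1.0. A model with change and the score alone gives about 6–20% false positives. Adding the first pH gives about 4–7%.

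**Step 5: can the data carry the model?** At an assumed hospital mortality of 20–40%, 346 × 0.20 ≈ 69 and 346 × 0.40 ≈ 138 deaths. With pH exposure, APACHE II, age and first pH (four parameters), that is 69/4 ≈ 17 to 138/4 ≈ 34 deaths per parameter before any exclusions.

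**The case against.** The best defence is that the mislabelled item alone is a one-line form error. Hospital and ICU deaths are recorded beside it, and the wording may be a slip for admission. That stands, and it limits the first part to correcting the item.

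Two stronger readings are tempting and are not supported.
- A reader might infer that goal 4 will be analysed on the discharge-anchored item, leaving a handful of events. No section assigns that item to goal 4.
- A reader might infer that goal 4 will use the predictor "Change of pH (between the lowest and highest pH") over the whole stay, so that length of stay alone creates an association with death. Section 8 defines that predictor only for the cardiac output model, at moments when output is also known. Nothing carries it over to goal 4. What the documents show is that the pH exposure for goal 4 is undefined.

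It is also fair to say that 5–83% spans the negligible and the severe, because every severity input is assumed. The range shows that the crude test is unprotected, not how biased this study would be.

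Finally, hospital death has no fixed follow-up length either. That is true. It is suggested because it counts in-hospital deaths and is already collected.

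**Conclusion.** The point holds for one secondary goal and one form item. Two findings rest on the text alone: the item's label and definition conflict, and no method listed for death adjusts for anything although severity and age are collected. These are firm.

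The size is illustrative only. With 346 patients, 30% mortality, no pH effect, severity–pH correlation 0.1–0.4 and severity effect 0.3–1.0 log-odds per SD, crude false positives run from about 5% to 83%. Adjustment for a score correlated 0.7 with true severity brings this to about 4–35%: less bias, not none. The primary goals and the sample size are not affected. It should be fixed before the data are analysed, while the outcome and exposure can still be chosen without sight of the results.

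**What to change.** 1. **Correct the item.** Either relabel it as death within 28 days after hospital discharge, for patients discharged alive only; or redefine it as death from any cause within 28 days of one fixed origin, counting in-hospital deaths. The second option needs date of death or day-28 status. The documents describe no source for these: Section 1 limits data to medical notes and ICU charts, and the enrolment log in Section 11 ("just a list of name, hospital number and study ID") identifies patients but does not record deaths.

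2. **Add a model for goal 4 to Section 8 and its copies.** Use logistic regression of hospital death on one prespecified pH exposure, measured in a fixed early window of PiCCO monitoring and adjusted for APACHE II and age. Follow-up for death starts at the end of the window. If the exposure is a change in pH, also adjust for the first pH. The investigators choose the exposure and window length; since their hypothesis concerns a level near 7.20, they should consider whether a level or a change serves it better. State how transfers to another hospital are counted.

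3. **State that residual confounding by severity remains.**

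**Cost.** One label, one extra model, and timed pH readings with the start of monitoring if these are not on pages not shown. Patients who die or leave before the window ends are excluded and counted. With assumed mean stays of 6–10 days, that would be about 2–15 of 104 deaths for a window of one to two days.
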